## 2 STUDY DESCRIPTION

### 2.1 Study Objectives

The primary objective of this study is:

- Compare the overall survival (OS) of patients treated with AEZS-108 to the OS of patients treated with doxorubicin.

The secondary objectives include:

- Compare efficacy based on progression-free survival (PFS), objective response rate (ORR) and clinical benefit rate (CBR).
- Compare safety.
- Determine the impact of these regimens on patient-reported quality of life during and for up to 1 year after completion of study treatment.
- Assess the pharmacokinetics and exposure-response relationships of AEZS-108, doxorubicin and doxorubicinol in a PK sub-study at selected sites and by sparse PK sampling, respectively.
- Assess the acute effects on electrocardiographic parameters (e.g., QT/QTc interval) within PK sub-study.

### 2.2 Study Design

This is an open-label, randomized, active-controlled, two-arm Phase III study to compare the efficacy and safety of AEZS-108 and doxorubicin. The study will include about 500 patients with advanced, recurrent or metastatic endometrial cancer who have

progressed and who have received one chemotherapeutic (i.e., cytotoxic) regimen with platinum and taxane (either as adjuvant or first line treatment).

Patients will be centrally randomized in a 1:1 ratio to receive treatment with either AEZS-108 (Arm A) or doxorubicin (Arm B).

During ongoing treatment, response will be evaluated every 3 cycles; earlier reassessments should be scheduled to verify a response (at least 4 weeks after first observation of the response) or in case of suspected progression. Patients, who have gone off-treatment for reasons other than progression, will be reassessed every 12 weeks until progression. All patients will be followed-up for survival.

On a regular basis, at intervals no longer than 6 months, results from safety analyses will be submitted to an independent Data and Safety Monitoring Board (DSMB) that will advise the Sponsor of potentially critical findings.

The final analysis will be performed after about 384 deaths have been observed. There will be two planned interim analyses; the first will be for futility only, the second will be for safety and efficacy.

Based on the availability of the assay for LHRH receptor expression in tumor specimens, subgroup analyses stratified for extent of LHRH receptor expression was planned to assess the predictive value of the LHRH receptor assay. Due to non-availability of a validated assay, no such stratified analyses can be performed.

### **2.3 Randomization and Blinding**

This is an open-label study.

## **3 ANALYSIS POPULATIONS**

### **3.1 Intent-to-Treat Population**

The Intent-to-Treat (ITT) population will consist of all randomized patients. Analyses of this population will assign patients the treatment they were scheduled to receive, regardless of any errors of dosing or dose modifications. Patients who received treatment in the group that is different from the one to which they have been randomized to, will be noted in the CSR.

### **3.2 Modified Intent-to-Treat Population**

A modified Intent-to-Treat (MITT) population will consist of all randomized patients, who received at least one dose of study treatment, i.e. the MITT population will exclude patients who never received study treatment.

### **3.3 Safety Population**

The safety population will include all randomized patients who received at least one dose of study treatment. In the safety analyses, patients will be included in the treatment arm that they have actually received. Patients who are included in a treatment group that is different from the one to which they have been randomized will be noted.

### 3.4 Per Protocol Population

The Per-Protocol (PP) population will include all randomized patients without major protocol deviations. What constitutes a major protocol deviation will be determined and documented prior to database lock. Protocol deviations will also be presented in the clinical study report.

## 4 GENERAL CONVENTIONS

Unless otherwise stated, all analyses will be performed using SAS Version 9.2 or higher and all hypothesis tests will be conducted at a two-sided significance level of 0.05. P-values will be presented with 3 decimals and p-values that are less than 0.001 will be presented as < 0.001.

Continuous (non-survival related) data will be summarized using descriptive statistics: number of observations (n), mean, standard deviation (SD), median, minimum, and maximum. Frequencies and percentages will be used to summarize categorical (discrete) data. Presentations of categorical data will generally suppress percentages for items where the count is zero in order to draw attention to the nonzero counts. In general, mean, standard deviation, median, 25th and 75th percentiles, minimum, maximum, and percentages will be presented with one decimal.

Unless otherwise stated, confidence intervals, when presented, will be constructed at the two-sided 95 % level. For binomial variables, the 95 % confidence intervals will be constructed using the normal approximation without continuity correction.

In the tables the following indication for treatment will be used: AEZS-108 and Doxorubicin. Data listings will show data presented in the summary tables by study drug, country, center and patient number.

### 4.1 Definition of Baseline

In general, the last observed measurement prior to first administration of study treatment will be considered the baseline measurement. In practice, for questionnaires, LVEF and ECG baseline is defined as screening visit. For laboratory parameters, vital signs and ECOG cycle 1 day 1 (C1D1) is considered as baseline. If C1D1 assessment is not available or if assessment on C1D1 is not before first treatment, screening value will be taken as baseline value. If date of first treatment is missing, screening value will be taken as baseline value.

### 4.2 Definition of Time

For the purpose of summarizing efficacy data, time will be defined relative to the date of randomization. Unless otherwise stated, for visits (or events) that occur on or after randomization, time is calculated as:

$$\text{time (days)} = \text{visit date (event date)} - \text{date of randomization} + 1.$$

For visits (or events) that occur prior to randomization, time is calculated as:

$$\text{time (days)} = \text{visit date (event date)} - \text{date of randomization to study treatment}.$$

For listings (such as for adverse events) of the quantity ‘days since first/last dose’ is defined as:

$$\text{days since first/last dose} = \text{event date} - \text{date of first/last dose.}$$

Events that occur on the same day as the first/last dose will therefore be described as occurring zero days from the first/last dose. In most cases, listings will include the number of days since first/last dose of AEZS-108/comparator (doxorubicin).

### **4.3 Tumor Assessment Schedule**

Tumor assessments will occur every 3 cycles ( $\pm 7$  days) during ongoing treatment, then if required beyond the end of treatment every 3 months ( $\pm 7$  days) while the patient is on study. The last assessment will occur when approximately 384 randomized patients have died.

### **4.4 Missing and Partial Data**

In general, other than for partial dates, missing data will not be imputed and will be treated as missing. The algorithms for imputation of partial dates vary depending upon the parameter and are presented in Section 12.4 (Appendix D - Imputation Rules for Missing Dates.)

### **4.5 Software**

Unless otherwise stated, all analyses will be conducted using SAS Version 9.2 or higher.

### **4.6 Changes to Planned Analyses**

Draft versions of the SAP will be numbered sequentially as Version x-1.0i. The final approved version will be numbered as Version x.0. The Clinical Study Report will document any change made after database lock.

## **5 DESCRIPTION OF THE STUDY POPULATIONS**

The paragraphs below specify presentations of data for both the ITT and safety populations. If, however, the two populations are almost the same (i.e., safety population is 95 % or more than the ITT population), then only the ITT tables will be presented. A summary of differences between the two populations will be noted in the CSR.

### **5.1 Disposition**

Patient disposition summaries will be presented by treatment arm and will include the number of patients enrolled, randomized, the number and percentage of randomized patients in the ITT, the modified ITT, the PP, and the safety populations. The summaries will also include the reasons for permanent discontinuation of study treatment and study. Disposition by investigational sites and by territory will also be presented. Trial territories are defined as follows:

- North America: US, CA;
- W/N-Europe/Israel: AT, BE, DE, DK, ES, FI, GB, IE, IL, IT, NL, NO, PL;
- Eastern Europe: BG, BA, BY, CZ, RU, UA, RO.

## **5.2 Demographic and Baseline Characteristics**

A summary of demographics and baseline characteristics will be presented by treatment arm for the ITT and safety populations.

The demographic characteristics consist of age, age category (defined below), sex, ethnicity, race, and Eastern Cooperative Oncology Group (ECOG) performance status. Baseline height and weight will also be presented using standard descriptive statistics.

Age (years) will be calculated as (date of informed consent – date of birth) / 365.25.

Age categories: < 65 years and 65 years or older, will be presented using frequencies and percentages.

The number and percentage of patients' ethnicity as well as reported race category will also be reported.

## **5.3 Medical History**

A data listing will present medical history. If useful for interpretation of the results of the study, a table will summarize the data.

## **5.4 History of Endometrial Cancer**

Tables will present information regarding the patients' history of endometrial cancer, including time since initial diagnosis to randomization, primary diagnosis. Summaries will be prepared for the ITT and safety populations and will display the information by treatment arm and overall. All details of endometrial cancer history (including origin of tumor specimen) will also be listed.

## **5.5 Baseline Comparisons**

The two treatment arms will be assessed descriptively for comparability of demographic and baseline characteristics. Data to be evaluated will include at least age, sex, race, and components of disease severity assessment and disease status (e.g., locally advanced, recurrent or metastatic endometrial cancer).

# **6 TREATMENTS AND MEDICATIONS**

## **6.1 Prior Treatment for Endometrial Cancer**

Use of prior treatment for endometrial cancer will be presented as subject frequency counts and percentages for the safety population. Descriptive statistics for type of drugs per patient will also be shown. Participants are only counted once for each type of therapy.

Prior chemotherapy will be coded using the World Health Organization (WHO) dictionary and summarized by treatment arms for the safety population;

- By WHO Drug base substance preferred name using frequency counts and percentages
- By regimen number using frequency counts and percentages on unique combinations of WHO Drug base substance preferred names.

For platinum and taxane based treatment the use as adjuvant or advanced treatment will be specified.

## **6.2 Prior and Concomitant Medications**

All medications recorded on the CRFs will be coded using the WHO dictionary. Prior and concomitant medications will be summarized by treatment arm in the safety population by anatomical therapeutic chemical (ATC) Class Level 4 and WHO Drug base substance preferred name. Participants are only counted once for each preferred term.

Prior medications are defined as medications with stop dates occurring before the date of first administration of any study treatment component. Concomitant medications are defined as medications with start dates occurring on or after the date of first administration of any study treatment component and no more than 30 days after the last administration of any study treatment. Medications with start and stop dates that bracket the date of first administration of any study treatment will be summarized as both prior and concomitant medications.

For the purpose of summarizing prior and concomitant medications, incomplete medication start and stop dates will be imputed as detailed in Section 12.4. Based on imputed start and stop dates, medications that clearly stopped prior to date of first administration of any study treatment component will be included in the prior medications table, and medications that clearly started on or after date of first administration of any study treatment component will be included in the concomitant medications table. All other medications will be included in both the prior and concomitant medications tables.

## **6.3 Study Treatment Exposure**

Study treatment exposure will be summarized by treatment arm in the ITT and safety populations.

The following will be summarized by treatment arm using descriptive statistics:

- number and percentage of patients who received at least one dose ('cycle')
- duration of exposure per patient, calculated as (date of last dose [start date of last cycle] – date of first dose [start date of first cycle] + 1),
- number of doses (cycles) received per patient,
- cumulative dose (in mg/m^2) received per patient,
- patients receiving prophylactic antiemetic treatment per treatment cycle, and
- patients receiving anti-allergic treatment per treatment cycle.

In addition, a table will be made summarizing duration of cycle 1 administration and duration of administration – all cycles combined.

## **6.4 Study Treatment Modifications**

Treatment modifications will be summarized by treatment arm in the ITT and safety populations for each randomly assigned study treatment.

The number and percentage of patients with doses delayed (withheld) and doses reduced, and reasons for these dose changes will be summarized by treatment cycle. The total number of dose delays and reductions will be shown.

## 6.5 Subsequent Anticancer Therapy

A summary of the number and percentage of patients receiving subsequent anticancer therapy after discontinuation of study treatment will be presented by treatment arm in the ITT population.

## 7 EFFICACY ANALYSES

### 7.1 Primary Efficacy Outcome – Overall Survival

The primary efficacy outcome is overall survival (OS).

#### 7.1.1 OS: Definition

OS is defined as the time from randomization to death for any cause during the study. Patients without confirmed vital status are censored on the day they are last known alive. Every reasonable effort will be made to establish vital status of each patient on the last day of the study, that is, the clinical cutoff date established after approximately 384 patients have died. OS will be calculated as follows:

For those who die during the study,

$$\text{overall survival (days)} = \text{date of death} - \text{randomization date} + 1;$$

For those who are alive or vital status cannot be determined at the end of the study,

$$\text{overall survival (days)} = \text{date of censoring} - \text{randomization date} + 1, \text{ with censor indicator indicating a censor.}$$

#### 7.1.2 OS: Primary Analysis

The primary analysis of OS will be performed using the ITT population.

The primary efficacy analysis will be performed using the ITT population. The final analysis, which is event-based, will be conducted after approximately 384 randomized patients have died. In the primary analysis, a log-rank test with an overall two-sided Type I error rate of 0.05 after taking the interim analyses into account will be used to compare OS between the two treatment arms via a SAS lifetest procedure. Kaplan-Meier estimates will be used to calculate median OS and the 95 % confidence interval of the median OS. The proportion of patients alive at six and 12 months (from randomization date) and the 95 % confidence intervals for these estimated proportions, if appropriate, will be presented.

A Cox model with treatment effects will be used to estimate the hazard ratio and perform hypothesis testing. The estimated hazard ratio and the 95 % confidence interval of the hazard ratio will be presented.

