8.3 Randomized allocation of study treatment

Patients who meet the eligibility criteria will be randomly allocated by central randomization in a 1:1 ratio to receive either AEZS-108 (Arm A) or doxorubicin (Arm B).

Start of study treatment (Cycle 1 Day 1) should be scheduled for the nearest feasible date, to ensure that screening investigations, in particular laboratory investigations or measurements, have been performed within 28 days prior to treatment start.

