### 7.1.3 Supportive and Sensitivity Analyses

To assess the robustness of the study results, supportive analyses of OS will be performed using modified ITT and per protocol population. In addition, the following sensitivity OS analyses will be performed, if appropriate:

Patients will be censored at the time when they received other non-protocol required anticancer treatment, if applicable.

Patients will be censored at the time when they drop out of the study due to AEs.

Exploratory analyses of the effect of baseline characteristics and other covariates will be conducted using Cox regression models. Cox models with treatment (forced into the model) and different (see listed underneath) covariates each at the time, and a global Cox model with treatment (forced into the model) and different covariates using backward selection will be made. The significance level to retain a variable in the model will be set at 10%. The following covariates will be considered:

- Age (entered as continuous covariate)
- Endometrial cancer type: Type I vs Type II  
Type I: endometrioid, squamous, adenocarcinoma (recorded under ‘other’)  
Type II: serous, clear cell, mixed, carcinosarcoma (recorded under ‘other’)  
(additional histology variants captured under ‘other’, will be assigned to Type I or II as medically appropriate)
- Histology: endometrioid vs serous vs clear cell vs squamous cell carcinoma vs other
- Tumor grade: Gx vs G1 vs G2 vs G3 vs G4 vs other
- Prior radiotherapy (yes vs no)
- Time since diagnosis (< 12 months vs  $\geq$  12 months)
- Stage of disease at study entry (advanced or recurrent disease vs metastatic disease)
- Potential center-effects  
Territory (North America vs W/N-Europe vs Eastern Europe)
  - North America: US, CA
  - W/N-Europe/Israel: AT, BE, DE, DK, ES, FI, GB, IE, IL, IT, NL, NO, PL
  - Eastern Europe: BG, BA, BY, CZ, RU, UA, RORecruitment volume (‘low recruiters’ vs ‘high recruiters’)
  - low recruiter: < 10 patients/site
  - high recruiter:  $\geq$ 10 patients/site

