## **7.5 Power and Sample Size Justification**

Approximately 384 events of deaths will be required to achieve 80 % power to detect a treatment difference at the overall two-sided 0.05 significance level after taking the planned efficacy/safety interim look into account. It is expected that approximately 500 patients will be enrolled during an estimated 24-month recruitment period and will then be followed for 12 months to observe a total of approximately 384 death events. In the sample size calculation, it is assumed that the median OS is 12 months for the group with investigational treatment (AEZS-108) and 9 months for the control group (doxorubicin). The sample size calculation has taken the interim analyses into consideration.

Based on published data on the pharmacokinetics of doxorubicin, a sample size of 20 patients for each arm is proposed, to provide a more detailed description than is currently available for the key pharmacokinetic parameters of AEZS-108, doxorubicin, and doxorubicinol. Based on preliminary pharmacokinetic data available from an ongoing study in bladder cancer patients, a variability of AEZS-108 similar to that for doxorubicin may be expected. Since collection of only a limited number of samples over a limited period (about 2-3 terminal elimination half-lives) is feasible within this sub-study, the comparison of the metabolite profiles will be orienting / exploratory / descriptive in nature.

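### The primary OS test and hazard ratio use no baseline prognostic factor; stratifying them by two factors already collected would protect or add power at little cost, although the stated 80% is not an error

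*SAP*

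**What the plan says.** SAP 7.1.2 and Protocol 9.4.2 set the primary OS analysis in the ITT population as "a log-rank test with an overall two-sided Type I error rate of 0.05 after taking the interim analyses into account". The effect estimate follows: "A Cox model with treatment effects will be used to estimate the hazard ratio and perform hypothesis testing". No stratum or covariate is named for either.

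Randomisation is described only as central and 1:1 (Protocol 8.3; SAP 2.2: "Patients will be centrally randomized in a 1:1 ratio"). SAP 2.3 says only that the study is open-label. No stratification factor is stated anywhere.

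Baseline factors appear in SAP 7.1.3: "Exploratory analyses of the effect of baseline characteristics and other covariates will be conducted using Cox regression models". They include age, cancer type (I or II), histology, grade, prior radiotherapy, time since diagnosis, stage at study entry and territory. They are entered one at a time, and then in a global model with backward selection at the 10% level.

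On power, SAP 7.5 states: "Approximately 384 events of deaths will be required to achieve 80 % power to detect a treatment difference", assuming median OS of 12 months on AEZS-108 and 9 months on doxorubicin.

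**The concern.** The trial enrols a mixed population: any histological subtype of endometrial adenocarcinoma, FIGO stage III or IV, recurrent or metastatic disease, prior chemotherapy as adjuvant or first-line treatment, and ECOG status 0 to 2 (Protocol 5.1 and 5.2). The sponsor lists cancer type and stage as covariates worth examining, yet the primary analysis does not use them and no document says that the randomisation did.

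When patients within an arm have different hazards, a log-rank test that ignores the difference works on an overall HR closer to 1 than the HR within each prognostic group. The stratified test works on the within-group HR. At stake is power that could be kept, or gained, with data the trial already holds. In addition, the plan has no adjusted OS analysis that is both non-exploratory and free of data-driven selection.

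**Working it through.** **1. Reproduce the plan's figure.** Inputs from SAP 7.3 and 7.5: medians 9 and 12 months, two-sided 0.05, 80% power, 384 deaths, final nominal p 0.049002, efficacy look at 192 deaths with nominal p 0.003051. With exponential survival the HR is 9/12 = 0.75.

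- Schoenfeld: 4 × (1.960 + 0.842)² / (ln 0.75)² = 380 deaths.
- Freedman: (1.960 + 0.842)² × (1.75/0.25)² = 385 deaths.
- Power at 384 deaths, final critical z = 1.9686: Φ(√384/2 × 0.2877 − 1.9686) = Φ(0.850) = 80.2%.
- Both looks together: 80.3%, overall two-sided alpha 0.0500.
- Expected deaths at 36 months ("approximately 500 patients will be enrolled during an estimated 24-month recruitment period and will then be followed for 12 months"): 205 + 182 = 387.

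The plan's figure reproduces.

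**2. Two readings of 0.75.** Suppose survival is exponential within prognostic groups with a within-group HR of 0.75. Treated survival at time t then equals control survival at 0.75t, so a control median of 9 months still gives a treated median of 9/0.75 = 12. The planning medians therefore fit a within-group HR of 0.75 as well as an overall HR of 0.75. Under the within-group reading, the average overall HR is nearer 1.

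**3. Power if 0.75 is the within-stratum HR.** Prognostic HRs and prevalences are assumptions; the documents give none. Simulation: 500 patients, 1:1, uniform accrual over 24 months, looks at 192 and 384 deaths, control median fixed at 9 months, 10,000 trials per row (Monte Carlo standard error about 0.4 points).

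| Assumed factors | Average overall HR | Unstratified | Stratified |
|---|---|---|---|
| None | 0.748 | 80.2% | 80.2% |
| One, HR 1.5, 30% | 0.751 | 79.1% | 80.6% |
| One, HR 1.5, 50% | 0.753 | 78.5% | 79.9% |
| Two, HR 1.5 each, 50% | 0.758 | 76.5% | 79.9% |
| One, HR 2, 30% | 0.760 | 75.6% | 79.5% |
| One, HR 2, 50% | 0.762 | 75.3% | 80.2% |
| One, HR 2.5, 30% | 0.768 | 73.1% | 80.5% |
| One, HR 2.5, 50% | 0.773 | 70.5% | 79.7% |
| One, HR 3, 30% | 0.776 | 69.1% | 79.7% |
| One, HR 3, 50% | 0.784 | 65.7% | 79.8% |

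Hand check from the average overall HR: at 0.762, Φ(9.798 × 0.2718 − 1.9686) = Φ(0.695) = 75.6%; at 0.773, Φ(9.798 × 0.2575 − 1.9686) = Φ(0.554) = 71.0%. Both agree with the simulation.

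Two factors each present in 40%, final look only (8,000 trials per scenario): HR 1.5 each, 76.9% unstratified and 79.7% stratified; HR 2 each, 70.1% and 79.5%; neither prognostic, 80.5% and 80.0%.

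**4. Power if 0.75 is the overall HR.** One factor at 50%, with the within-group HR lowered so that the average overall HR is about 0.75:

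| Factor HR | Within-group HR | Unstratified | Stratified |
|---|---|---|---|
| 1.5 | 0.745 | 80.1% | 81.7% |
| 2 | 0.739 | 78.8% | 83.8% |
| 2.5 | 0.728 | 78.5% | 86.5% |

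**5. Type I error.** With no treatment effect and a factor of HR 2.5 at 50%, one-sided rejection was 0.027 unstratified and 0.028 stratified, against a nominal 0.025.

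**The case against.** An unstratified ITT log-rank test is pre-specified and valid, its power figure reproduces, and no two passages conflict. This stands: the point is an improvement in efficiency, not the repair of a mistake.

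The size has no source in the documents. Protocol 1.1 puts endometrioid histology at about 80% of endometrial cancers in general. That suggests Type II may be less common than the 30–50% used above, although it does not describe the trial's population. With one factor at 20% prevalence, two separate runs of 4,000 trials each put unstratified power for HR 1.5 at 78.5% and 79.6%, against 78.5% and 80.5% stratified; HR 2 gave 76.5% against 80.2%. Mild or uncommon factors therefore cost little.

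Three stronger readings are tempting and are not supported:

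- *The stated 80% is wrong, or holds only if all patients in an arm share one hazard.* It holds for an overall HR of 0.75 whether or not patients differ.
- *Power is 70–77%.* That range needs the within-stratum reading together with particular prognostic strengths that the documents do not give.
- *Chance imbalance biases the hazard ratio.* For a factor present in 40%, the standard error of the difference between arms is √(2 × 0.4 × 0.6/250) = 4.4 points, so the 95% range is ±8.6 points. With a prognostic HR of 2, that extreme moves the log HR by 0.086 × 0.693 = 0.06. The corresponding standard error is 0.03, against 2/√384 = 0.10 for the log HR itself. This is ordinary random error, already inside the power figures above.

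The single-covariate Cox models of SAP 7.1.3 involve no selection and would show whether either factor matters. They are exploratory, however, and do not replace a pre-specified primary test.

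Timing also counts. SAP version 4 is dated March 2017, the trial is open-label, and the documents do not say whether the 192-death look has taken place. A late change of primary test would be open to challenge.

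**Conclusion.** The point holds as a low-cost improvement. The primary OS test and hazard ratio use no baseline factor, although suitable ones are collected and listed.

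If the within-stratum HR is 0.75, unstratified power is about 76–79% with one or two factors of HR 1.5 and about 70–76% with strong factors (one of HR 2 to 2.5, or two of HR 2 at 40% each), falling to 66–69% for a single factor of HR 3. A stratified test gives about 79–81% throughout. If the overall HR is 0.75, the plan's 80% stands and stratifying lifts power to about 82–86%. Stratifying is therefore level or better on both readings whenever a factor is prognostic.

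The figures assume exponential survival within strata, a constant within-stratum HR, uniform accrual and no dropout from OS follow-up. The prognostic strengths and prevalences are assumptions that the sponsor should replace with its own.

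**What to change.** In SAP 7.1.2, make the log-rank test and the Cox model stratified by two factors from SAP 7.1.3: cancer type (I or II) and stage at study entry (advanced or recurrent versus metastatic). In addition:

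- Assign every histology to a type before database lock, without sight of outcome or treatment arm. SAP 7.1.3 leaves unlisted variants to medical judgement, and several subtypes eligible under Protocol 5.1 (mucinous, transitional cell, small cell, undifferentiated) are not placed in either type.
- Keep the unstratified test and Cox model as a sensitivity analysis.
- Use the same strata for PFS (SAP 7.2.5) and for the Mantel-Haenszel ORR test (SAP 7.2.2), which now names none.
- Align the protocol synopsis and Protocol 9.4.2, which carry the same unstratified test. Protocol Section 9 allows methods to be updated in the SAP, but the texts would otherwise differ.
- Use the same test at the 192-death look and at the final analysis. If that look has already used the unstratified test, keep it as primary and pre-specify the stratified analysis, with these two fixed factors and no backward selection, as the leading supportive analysis.

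Cost: SAP and protocol wording, the assignment of histologies, and about half a point of power if neither factor is prognostic (80.5% against 80.0%). The reported HR becomes a within-stratum HR and should be labelled as such.
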